Many patients are members of the same family. As such, the research team will assemble family units (using household address, primary telephone number, patient ID of the guarantor, and insurance member ID as the variables of commonality to create these family units). For RCT 1, for each family, 1 individual will be randomly selected as the index patient. Only index patients who are also active portal users and affiliated with a primary care practice (criteria explained below) will have their data analyzed as part of the primary analysis plan. Secondary analyses will involve all study subjects.

Gender and age: We anticipate the gender distribution to be roughly equal. All ages of patients will be included in the study; however, patient will not receive a message until they are 6 months of age, as the flu vaccine is not recommended for those less than 6 months of age.

Racial and ethnic origin: There are no enrollment restrictions based on race/ethnicity.

Inclusion criteria

A patient at one of the clinics of interest within the UCLA Health System (up to 55 practices). An individual is deemed a primary care patient of the UCLA Health System through the following algorithm:

Assigned managed care patients (UCLAMG) + Attributed patients from other payers/ACOs

- ≥ 2 PCP visits in the past 3 years; or

- ≥1 PCP visit with preventive service code in past 1 year (99381-99397 or G0438/G0439)
- All visits cannot be urgent care visits (ie excludes visits after hours or on weekends, not by urgent care codes since UCLA does not bill accordingly)

Active patient: We decided to use the algorithm outlined above and currently approved and in place by the UCLA Health System as the research team believes it to be a generalizable model that could be applied to other health systems.

Exclusion criteria

Patients will be excluded from the overall study if they are not part of UCLA's primary care registry per the above algorithm detailed in the inclusion criteria.

Creating family units

An overall address field will be constructed from the data pull including the address, city, state, and zip code fields. Primary telephone number, patient ID of the guarantor and insurance member ID will be used as other variables in the process to create the family units. The following steps taken to create these family units is described below:

1. Start with a single entry in the contact data pull
2. Add any other entries with the same patient ID as any existing entry to the family

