METHODS AND STUDY PROCEDURES

The UCLA Health System is made up in part of approx 55 primary care practices. The leadership team at UCLA Health has agreed to allow these practices to participate in the 4 RCTs outlined below. Among the primary care practices (up to n= 55), patients who meet the inclusion criteria (outlined above and in section 11.1 item 4.0) will be randomized into the study arms. Below is a detailed outline of each of the four RCTs and the interventional components.

RCT - conducted 2018-19

We propose a randomized trial, where patients are randomized within practices to 0, 1, 2 or 3 R/R messages sent via the portal on a 1:1:1:1 basis. Our prior studies showed the effects of influenza R/R can vary by patient and practice factors (i.e. age, race, practice type). We will select 1 adult or 1 child per household to be the index patient for randomization since family members can affect each other's receipt of vaccine. Inclusion criteria: Outlined above.

Eligibility for R/R: Our EHR will identify subjects who are eligible for either 1 or 2 influenza vaccinations based on ACIP algorithms (2 are recommended for children <9 years who have not had a prior flu vaccination). Spacing of R/R messages: Based on our prior studies, we plan to send up to 3 R/R messages, spaced every 3-4 weeks, beginning in October; Aim 1 findings may modify plans.

Languages: R/R messages will be in English. Portal messages in Spanish will not be available during RCT 1 due to technological capabilities.

Health Literacy: We will use plain language <8th grade reading level per Flesch-Kincaid analysis. In Aim 1 we will adapt messages with input from key stakeholders (see IRB submissions titled: Patient Portal - Patient Qualitative Interviews and Patient- Portal Provider Qualitative Interview for full outline of protocol). Our message content will be rooted in decades of work by vaccine communication expertise and rooted in the Health Beliefs Model (see file named: Health Belief Model for multiple examples of the content that will be adapted for the message). The content of the R/R message will be the same for each reminder that is sent. Please see item 1.0 for the language to be used in the messages. Please note, the file titled RCT #1 Reminders is the language used in the first two reminders (sent in October and November 2018), and the file titled RCT #1 Reminders_December is the language for the third and final reminder to be sent in December 2018 for RCT #1.

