Patient variables will include - age (6m-17y, 18-64y, 65+y), race/ethnicity, gender, primary language (by EHR), degree of portal use, and receipt of influenza vaccination in prior years. We recognize few UCLA patients have Medicaid; we will focus on low-income groups in the dissemination phase (Aim 3).

Dependent Measures

Vaccine Outcome: The primary outcome is influenza vaccination during the vaccination season as measured by analysis of EHR data. For children <9y who had not received prior influenza vaccination, the outcome will be at least 1 influenza vaccination.

Process Outcomes: These will include: (a) total # visits to the practice during the study time period, (b) # flu vaccine or nurse visits, and (c) missed opportunities. Visits will be measured by the EHR; using ICD-10/CPT codes to classify visits to primary care as preventive, acute/chronic, or nurse-vaccination. Missed opportunities are defined as # vaccine-eligible visits during which the patient did not receive an influenza vaccination. These process metrics will help assess how the intervention worked.

Additional Measures: see file: Summary of outcome measures RCT 1 which shows additional measures, grounded in the RE-AIM framework. Found in item 1.0 of this section.

Costs: Since the intervention is implemented centrally we assume no added practice costs. We also assume practice costs/vaccination from portal R/R is identical to standard practice costs/vaccination. We will assess the time and costs of study and implementation personnel and non-personnel costs, distinguishing planning costs from intervention costs. We will measure costs using a standardized time study/resource survey sent weekly to all individuals working on the study that delineates (a) the # hours spent for each individual, and (b) research vs implementation time. We will use national salary estimates by work code from the Bureau of Labor Statistics to value personnel time in standard rates. We will measure non-personnel costs EHR hardware, software, materials.

Cost and Cost Effectiveness

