Costs: We will assume that the actual per-dose vaccination costs (administration costs, vaccine costs, storage, etc.) are identical for intervention and comparison patients and equal to the average national reimbursement for an influenza vaccine dose. The difference in total costs between the study arms will be influenced by the total costs of implementing the intervention, the difference in vaccination rates within study arms, and the subsequent health care utilization by the population (which we can model from prior studies)

Effectiveness: For each RCT we will estimate effectiveness using model-based, standardized expected values (mean) at the end of each RCT. We will calculate incremental cost-effectiveness ratios (ICERs) for each intervention arm.

For example, to compare costs in RCT #1 for Arm 3 R/R's vs Arm 2 R/R's, the ICER is: $ICER (\text{Arms 3 R/R vs 2 R/R}) = (\text{costArm 3 R/R} - \text{costArm 2 R/R}) / (\text{Flu vaccine rateArm 3 R/R} - \text{Flu vaccine rateArm 2 R/R})$

In the numerator of the above equation, the costArm X is equal to [(# Flu vaccine doses given per study arm x average national vaccine reimbursement per dose) + average costs per patient in that Arm]. The denominator of the equation is the difference in model-based, standardized expected values at the end of the intervention.

STATISTICS AND ANALYTIC PLAN

Analytic Plan:

The primary outcome is receipt of influenza vaccine among eligible index patients comparing the effectiveness of 1, 2, or 3 MyChart flu reminders to zero MyChart flu reminders.

Secondary measures are receipt of influenza vaccine among all identified patients in the primary care registry (per the algorithm outlined above in the inclusion criteria), process metrics, # subsequent preventive visits, and costs.

Power Analysis:

Power was evaluated using a simulation study. We assumed a within-practice randomization plan, and expect at minimum the sample sizes reported in Table 3 (n=145,684). We further assumed, based on preliminary UCLA Health data, that influenza vaccination rates are 42% among portal users without receipt of any portal-based R/R, and 45%, 47% and 49% among users in the 1, 2, and 3 R/R arms. We estimate 1,248 portal user families per practice (we will select 1 subject per family), based on our estimated mean family size of 2.38 portal users per family, and up to 55 practices.

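### The plan sets no season start date and no rule for patients vaccinated before the first October reminder, which costs precision on the 2-point consecutive-arm contrasts

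*Combined protocol and SAP*

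**What the plan says.** Under Dependent Measures, the Vaccine Outcome paragraph reads: "The primary outcome is influenza vaccination during the vaccination season as measured by analysis of EHR data". No calendar window follows.

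Under Methods and Study Procedures, the 2018-19 RCT section sets the timing of the intervention: "we plan to send up to 3 R/R messages, spaced every 3-4 weeks, beginning in October". It also mentions "the third and final reminder to be sent in December 2018 for RCT #1". The allocation is described as "patients are randomized within practices to 0, 1, 2 or 3 R/R messages sent via the portal on a 1:1:1:1 basis".

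Three places bear on whether patients already vaccinated are analysed:

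- Exclusion criteria: "Patients will be excluded from the overall study if they are not part of UCLA's primary care registry". This is the only exclusion.
- Selection of the index patient for primary analysis: three conditions (active portal use, affiliation with a study practice, random selection within the family). None concerns current-season vaccination.
- Eligibility for R/R: "Our EHR will identify subjects who are eligible for either 1 or 2 influenza vaccinations based on ACIP algorithms". This governs messaging and is not written as a condition for entering the analysis.

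The Power Analysis states its control assumption as follows: "influenza vaccination rates are 42% among portal users without receipt of any portal-based R/R". For one, two and three reminders it takes 45%, 47% and 49%. It does not say what window these rates cover.

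**The concern.** A dose given before the first message cannot depend on how many messages a patient was assigned. If the season opens before October, such a patient is a fixed success in every arm. If it opens at the first send and the patient stays in the denominator, the patient is a fixed failure in every arm. Either way the patient adds variance and tells us nothing about reminders. Two analysts could also build different primary datasets from this text.

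What is at stake is precision. Hyp. 2a.2 tests consecutive arms with a Bonferroni correction. The plan quotes its power for a 3-point step, yet two of its three assumed steps are only 2 points (45% to 47%, 47% to 49%). The same tests are repeated within age and race/ethnicity strata. The odds ratio is affected in meaning as well: with early doses counted as successes, it is closer to 1 than the odds ratio among patients who could still respond.

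**Working it through.** **Inputs.** From the Power Analysis: rates 42%, 45%, 47% and 49%; 1,248 × 55 = 68,640 index patients. At 1:1:1:1 that is 17,160 per arm, or 17,160 vs 51,480 for the pooled contrast. From the Primary Outcome analysis: two-sided 0.05, with Bonferroni for consecutive arms (taken here as three contrasts, 0.05/3, critical value 2.394). The share f vaccinated before the first send is **an assumption** (5% to 20%).

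**Formula.** SE = √[p₁(1−p₁)/n₁ + p₂(1−p₂)/n₂]; z = (p₂−p₁)/SE; power = Φ(z − critical value). There is no covariate adjustment. Randomization is within practice, so the 1% ICC costs nothing: a variance factor of 0.99 moves 90.7% to 91.0%.

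**The plan's own figures.**
- 42% vs 47%, pooled (mean of 45, 47 and 49 is 47): SE = 0.00436, z = 0.05/0.00436 = 11.46, power about 100%. This agrees with the stated figure of over 90%.
- 42% vs 45% (OR 1.13) at 0.05/3: z = 5.61, power 99.9%. This also agrees.
- 45% vs 47% at 0.05/3, not quoted in the plan: SE = √[(0.2475 + 0.2491)/17,160] = 0.00538, z = 3.72, power 90.7%. For 47% vs 49% it is 90.6%.

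**Removing early-vaccinated patients equally from all arms.** If the planning rates include early doses, each rate becomes (p−f)/(1−f) and each arm n(1−f). For 45% vs 47%:

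| f | Rates | n per arm | z | Power |
|---|---|---|---|---|
| 0 | 45.0 / 47.0% | 17,160 | 3.72 | 90.7% |
| 5% | 42.1 / 44.2% | 16,302 | 3.84 | 92.6% |
| 10% | 38.9 / 41.1% | 15,444 | 3.99 | 94.4% |
| 20% | 31.3 / 33.8% | 13,728 | 4.42 | 97.9% |

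The squared ratios of the z statistics (before rounding) give effective sample size gains of 7%, 15% and 42%.

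Keeping these patients as failures (rates p−f, n unchanged) gives 92.9% at f = 10% and 96.6% at f = 20%. Exclusion does better than either way of keeping them.

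**Primary contrast, 42% vs 47%.** At f = 5%, 10% and 20% the still-due difference is 5.26, 5.56 and 6.25 points, and the OR is 1.24, 1.27 and 1.34 (1.22 with everyone kept). z rises from 11.46 to 11.88, 12.40 and 13.99. Power is about 100% throughout.

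**Link between the two effects.** All-patient difference = (1−f) × still-due difference: 0.90 × 5.56 = 5.0 and 0.80 × 6.25 = 5.0.

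**Sensitivity of the 45% vs 47% result.**
- *Sample size.* Dividing the plan's other total, 145,684, by its mean family size of 2.38 gives about 61,212: power 86.8% with everyone kept, and 89.1%, 91.5% and 96.3% at f = 5%, 10% and 20%. If all 145,684 were index patients, power with everyone kept would be 99.9%.
- *Subgroup.* For an illustrative stratum with half of 68,640, still at 0.05/3: 59% with everyone kept, 66% at f = 10%, 77% at f = 20%. Actual stratum sizes are not given.
- *Meaning of the rates.* If 42-49% described only patients unvaccinated in October, counting early doses would shrink the step to 0.90 × 2 = 1.8 points (f = 10%) or 0.80 × 2 = 1.6 points (f = 20%). Power at 68,640 would be 82.7% or 72.5%. The primary contrast would stay at about 100%.

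**The case against.** A reader might infer four stronger claims. The documents support none of them.

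1. *The outcome counts pre-October doses.* The text does not say so. This is an inference from an undefined season. The phrase about eligible index patients in the Analytic Plan might even be meant to exclude those already vaccinated, although the listed index criteria do not.
2. *The primary comparison loses power.* It does not: power is about 100% at every f tried.
3. *The effect is biased.* Early vaccination is balanced across arms in expectation. Five points is a correct season-coverage effect in all index patients, which suits the stated aim of raising immunization rates across the health system and the intent-to-treat analysis.
4. *The cost-effectiveness ratio is distorted.* If costs and doses are counted per patient on the same patients, the incremental cost and the incremental rate both scale by 1/(1−f), so the ratio does not move.

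The other side adds that the gain on the 2-point contrasts is modest and rests on an unknown f. At f = 20%, 20 of the 42 control points, or 48% of control vaccinations, would precede the first message. If the 42-49% rates are season-long, the planned power already allows for early doses. All of this stands.

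One further caution also stands. A filter on EHR dose dates is safe only if the list is frozen at first send. Doses given elsewhere could be entered later with earlier dates, perhaps after a reminder prompts the patient to report one, and the record would then depend on arm. The documents do not say whether this happens.

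What the objection does not answer is that the window and denominator of the primary outcome are open. It also does not answer that the season-coverage effect can be estimated with a smaller standard error: at f = 10%, (1−f) × 0.00557 = 0.00502, against 0.00538 with everyone kept.

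**Conclusion.** The point holds as a gap in definition with a moderate cost in precision. The plan does not date the season and has no rule for patients vaccinated before the first reminder, so they appear to remain in the primary analysis set. For 45% vs 47% at 68,640 and 0.05/3, removing them would raise power from 90.7% to between 92.6% and 97.9% for f between 5% and 20%. This rests on an assumed f, on planning rates that include early doses, on three Bonferroni contrasts and on unadjusted proportions. The model's adjustment for prior-year vaccination could already absorb part of the noise. The pooled primary test, the all-patient risk difference and a consistently computed cost-effectiveness ratio remain valid. It is worth correcting because the change is cheap, not because the main result is at risk.

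**What to change.** - State the start and end dates of the season.
- Fix one common first-send date for all four arms, control included. Using each arm's own reminder dates would break comparability.
- At that date, freeze the EHR list of patients with a recorded current-season dose. Later entries do not alter it.
- Pre-specify the analysis of Hyp. 2a.1 and 2a.2 among index patients not on the list, counting doses from that date to season end.
- Also report the full-season effect in all index patients, which equals (1−f) times the still-due risk difference, with f the share on the frozen list.

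The cost is SAP wording and one saved EHR extract, with no new data collection. The downside is that the odds ratio then describes patients still due at first send, so both results should be shown.

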Adjusting for clustering of patients in practices, and assuming an intraclass correlation (ICC) of 1% (consistent with previous work), this sample size provides >90% power to detect an overall difference of 5 percentage points between portal-based R/R (combining 1, 2, + 3 R/R arms) and 0 R/R arm for all users and subgroups of interest (age and race/ethnicity). The power for the subgroups corresponds to evaluating the treatment effect within each subgroup. These power analyses represent conservative estimates based on the available patient sample—we expect larger effect sizes based upon our prior R/R studies. An estimated number of index subjects is $1,248 \times 55 = 68,640$.

Statistical Analysis- Primary Outcome

Hyp. 2a.1: Patients receiving 1, 2, or 3 portal R/R will have higher influenza vaccination rates than 0 R/R.

Primary outcomes (patient receipt of flu vaccine) are binary; our main explanatory variable will be an indicator for the receipt of any portal-based R/R.

We will employ intent-to-treat analyses using mixed effects logistic regression models with practice random effects, an approach recommended for RCTs in which the goal is to estimate the causal effects of interventions on individuals, adjusted for patient correlation within practice. In addition to the treatment variable, the covariates in the model will include patient age (6m-17y, 18-64y, 65+y), race/ethnicity, gender, primary language, degree of portal use, flu vaccination in prior year, and practice type (internal medicine, family medicine, pediatric). This method performs well in situations where the number of observations per cluster is large and for unequal cluster sizes. Hypothesis tests will be two-sided and a p value < 0.05 will be considered statistically significant. We will use SAS v9.4 (SAS Institute Inc., Cary, NC).

Hyp 2a.2: More R/R messages will incrementally increase vaccine rates (3 R/R > 2 R/R > 1 R/R > 0 R/R): As above, we will use mixed effects logistic regression models.

The major difference for these analyses is that we will test for pairwise differences between consecutive study arms. With linear contrasts we can determine if each additional R/R increases vaccination rates. Bonferroni corrections will be applied to account for multiple comparisons. The expected sample size provides >90%

power to conservatively detect an OR of 1.13 between consecutive study arms (corresponding to a 3% increase in vaccination rates from the baseline rate of 42%).

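### The ICER takes vaccine cost from observed dose counts but effectiveness from covariate-standardised rates, which adds avoidable noise to the vaccine-cost part, and no interval is planned

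*Combined protocol and SAP*

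**What the plan says.** All of the ICER text is in the combined protocol and SAP, under Cost and Cost Effectiveness. The worked example compares the 3-reminder arm with the 2-reminder arm. Each arm's cost is built from "Flu vaccine doses given per study arm x average national vaccine reimbursement per dose) + average costs per patient in that Arm". On effectiveness the section says "we will estimate effectiveness using model-based, standardized expected values (mean) at the end of each RCT", and it defines the bottom of the ratio the same way: "The denominator of the equation is the difference in model-based, standardized expected values at the end of the intervention".

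Statistical Analysis- Primary Outcome gives the adjusted model. Besides age, race/ethnicity, gender and language, its covariates include "degree of portal use, flu vaccination in prior year, and practice type (internal medicine, family medicine, pediatric".

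No section says that the dose count is standardised, gives the share of outcome variance the covariates explain, states a price per dose, or names a method for the uncertainty of the ICER.

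**The concern.** The section assumes one cost per dose, identical in every arm. Put the formula on a per-patient scale and suppose one dose per vaccinated patient. Each extra vaccination then costs one reimbursement, so the vaccine-cost part of the ICER is a known constant. The plan instead multiplies the reimbursement by an unadjusted rate difference and divides by an adjusted one. If one arm happens to hold more people who were vaccinated last year, its dose count rises, while standardisation takes most of that rise out of the denominator. A quantity that the plan's own assumption fixes becomes a random one.

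The second gap is that the ratio is planned as a single number, although its denominator for 2 v 1 and for 3 v 2 is a planned step of only 2 points. Aim 2 includes costs, and the toolkit is to carry cost information to other health systems. A ratio reported without an interval would look more precise than it is.

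**Working it through.** **Inputs from the plan**
- Power Analysis assumes a control-arm rate of 42%. For the reminder arms its assumption is "45%, 47% and 49% among users in the 1, 2, and 3 R/R arms". The 3-v-2 step is therefore 49% - 47% = 2 points.
- Index patients: 1,248 x 55 = 68,640, which reproduces the plan's figure. Allocation is 1:1:1:1, so 68,640 / 4 = 17,160 per arm.
- The other total in Power Analysis: 145,684 / 4 = 36,421 per arm.

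**Assumption.** R2, the share of outcome variance explained by the covariates, is not given. I use 0.10 to 0.36.

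**The plan's own figures.** The plan states no ICER or ICER error to reproduce. The related power statement does reproduce: (0.45/0.55) / (0.42/0.58) = 1.13. At 17,160 per arm and alpha 0.05/3 (my reading: three consecutive contrasts), power is 99.9% for 42 v 45 and 90.6% for 47 v 49.

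**Step 1: the algebra.** Let c be the reimbursement per dose. Per patient, with one dose each:
- as written, the vaccine-cost part is c x (raw difference) / (standardised difference);
- on one basis, it is c x (standardised difference) / (standardised difference) = c.

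**Step 2: noise in the raw difference.** At 17,160 per arm, SE = sqrt((0.47 x 0.53 + 0.49 x 0.51) / 17,160) = 0.00539, or 0.54 points. That is 27% of the 2-point step. At 36,421 per arm the SE is 0.0037, or 18.5% of the step.

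**Step 3: size of the mismatch.** SD(raw - standardised) = sqrt(R2) x SE. Divided by the 2-point step:

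| R2 | 17,160 per arm: 1 SD / 95% limit | 36,421 per arm: 1 SD / 95% limit |
|---|---|---|
| 0.10 | 8.5% / 16.7% | 5.9% / 11.5% |
| 0.20 | 12.1% / 23.6% | 8.3% / 16.2% |
| 0.30 | 14.8% / 28.9% | 10.1% / 19.9% |
| 0.36 | 0.6 x 27% = 16.2% / 31.7% | 0.6 x 18.5% = 11.1% / 21.8% |

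**Step 4: simulation check.** 600 trials per setting, one binary prior-vaccination covariate (assumed prevalence 45%), a logistic model with standardisation, and no practice effects. The 95% range of raw/standardised:
- 17,160 per arm: 0.71-1.28 at R2 = 0.25, and 0.64-1.36 at R2 = 0.36;
- 36,421 per arm: 0.81-1.18 and 0.78-1.23.

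The mean raw and mean standardised differences were both about 0.020, so there was no systematic bias.

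**Step 5: the missing interval.** At R2 = 0.25 and 17,160 per arm, the adjusted SE is 0.00539 x sqrt(0.75) = 0.00467. The 95% CI is 2 +/- 1.96 x 0.467 = about 1.1 to 2.9 points (1.085 to 2.915). Programme cost per extra vaccination varies as 1 / difference, so it spans 2 / 2.915 = 0.69 to 2 / 1.085 = 1.84 times its point value.

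**The case against.** A reader might infer that the vaccine-cost part is simply wrong by about 30%. The documents do not support that. A 30% mismatch means raw and standardised differences 0.6 points apart. At 17,160 per arm that is the 95% limit only if R2 is about 0.32, a figure the plan does not give. The chance of exceeding it is 1.3% at R2 = 0.20 and 4.2% at 0.30. At 36,421 per arm, R2 would have to be about 0.68. The costing population is not stated; with the whole registry (385,000 / 4 = 96,250 per arm) and R2 = 0.30, the 95% limit is 12.2%.

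Nor is this bias, since randomisation makes both differences estimate the same quantity. A sign change is also not a realistic worry at the planned effect: 0.02 / 0.00539 = 3.7 SE from zero, a probability of about 0.0001.

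Three further objections have weight.
- What distinguishes a third reminder from a second is programme cost per extra vaccination, which the dose-count mismatch does not touch. Without a dose price or programme cost, the error in the whole ICER cannot be stated.
- Counting doses has a purpose. Two are recommended for some children under 9, while the outcome counts at least one.
- The formula also adds an arm total to a per-patient average, so it must be rewritten anyway, and cost is a secondary measure with no hypothesis test.

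These limit the size and reach of the point. They do not remove it. Correcting the units alone would leave two estimators in one ratio, and a single trial yields a single ICER, so its reader receives the noise. The missing interval does not depend on the mismatch at all.

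**Conclusion.** The point holds with limited size. Followed as written, and once put on a per-patient scale, the plan adds avoidable random error to the vaccine-cost part of the ICER. The percentages in Step 3 rest on the assumed R2 range, the planned 47% and 49%, equal arms, and one dose per vaccinated patient. They describe noise in one part of the ratio and should not be read as the error of the whole ICER.

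The absence of an interval is the firmer half: under the plan's smaller sample size and R2 = 0.25, the programme-cost part is uncertain by nearly a factor of two upwards. Both are worth correcting before analysis. Neither touches the primary comparison.

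**What to change.** 1. When the formula is rewritten per patient, define each arm's vaccine cost as standardised vaccination rate x mean doses per vaccinated patient x reimbursement per dose. Use the same population as the denominator, and state which population that is. Pool the mean doses over arms and show a by-arm version as a sensitivity analysis; a by-arm mean in the main calculation would let dose-count noise back in.
2. Bootstrap the whole calculation, resampling index patients within practice and arm and refitting the model each time. Report each ICER with a 95% interval. If the interval for a rate difference includes 0, report incremental net benefit instead of the ratio, over a stated range of values per extra vaccination, since the plan gives none.

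The cost is SAP wording and some programming, with no new data. The downside is that the pooled figure assumes mean doses per vaccinated patient do not differ by arm, which the sensitivity analysis would check.

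### Do the 68,640 index subjects in the power analysis contradict the stated minimum of 145,684 and the family size of 2.38?

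*Combined protocol and SAP*

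**What the plan says.** The Power Analysis section gives four figures:

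- A minimum sample: the authors "expect at minimum the sample sizes reported in Table 3 (n=145,684"). The unit is not stated, and Table 3 is not in the text available for review.
- Families: "We estimate 1,248 portal user families per practice (we will select 1 subject per family), based on our estimated mean family size of 2.38", together with a practice count worded as an upper limit ("2.38 portal users per family, and up to 55 practices").
- Assumed vaccination rates: 42% with no reminder, and "45%, 47% and 49% among users in the 1, 2, and 3 R/R arms".
- The analysed total: "An estimated number of index subjects is" 1,248 x 55 = 68,640.

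Two power statements follow. For the pooled comparison of any reminder with none, "this sample size provides >90% power to detect an overall difference of 5 percentage points", in all users and in the age and race/ethnicity subgroups. For Hypothesis 2a.2, "we will test for pairwise differences between consecutive study arms" with Bonferroni correction, and the sample is said to give more than 90% "power to conservatively detect an OR of 1.13 between consecutive study arms", which the plan equates to 42% versus 45%.

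**The concern.** The three inputs look as though they should form a chain: users divided by users per family gives families, and families divided by practices gives families per practice. Read that way, the chain breaks. Dividing 145,684 by 2.38 gives about 61,200 families, or 1,113 per practice over 55 practices, not 1,248. The printed 1,248 does fit if the practice count is 49, which suggests that a per-practice figure worked out for 49 practices was later multiplied by 55.

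The primary analysis uses one index patient per family, so this total is the planned analysed sample. An overstatement of 12% would inflate the per-arm numbers (17,160 against 15,303) and could weaken the power claims. It is also unclear whether the sample size behind those claims is 145,684 or 68,640.

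**Working it through.** **Inputs.** From the Power Analysis: 145,684; 2.38 users per family; 1,248 families per practice; up to 55 practices; rates of 42%, 45%, 47% and 49%. From the methods for the 2018-19 trial: 1:1:1:1 allocation within practices. From the sections on active portal users and index patients: a registry of 385,000, of whom about 59% are portal users. From the primary-outcome analysis: two-sided alpha 0.05.

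**The plan's own figure.** 1,248 x 55 = 68,640. The printed product is exact.

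**The chain, if 145,684 counts portal users.**
- Families: 145,684 / 2.38 = 61,212 (61,083 to 61,341 as 2.38 runs from 2.385 to 2.375).
- Per practice: 61,212 / 55 = 1,113.
- Ratio: 68,640 / 61,212 = 1.121, a difference of 7,428.
- Family size implied at 55 practices: 145,684 / 68,640 = 2.12.
- Practices implied by 1,248: 61,212 / 1,248 = 49.05.

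**How strong is the match at 49?** 145,684 / 1,248 = 116.73. Dividing by 2.385 and by 2.375 gives 48.95 to 49.15, a width of about 0.21. An interval that wide holds some whole number about one time in five by chance. The number 49 appears nowhere in the documents.

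**Is 68,640 out of reach?**
- Users needed: 68,640 x 2.38 = 163,363.
- Users available on the plan's other figures: 385,000 x 0.59 = 227,150, or 227,150 / 2.38 = 95,441 families.

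The requirement lies above the stated minimum and well below the registry-based figure.

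**Does power depend on the total?** I used z = difference / sqrt(p1(1-p1)/n1 + p2(1-p2)/n2). There is no design-effect inflation, because randomisation is within practice, and no covariates. The pooled reminder rate is (45 + 47 + 49)/3 = 47%. The plan does not give the Bonferroni divisor; I assumed three consecutive contrasts.

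| Contrast | Alpha | 61,212 | 68,640 |
|---|---|---|---|
| 42% v 47%, 1:3 | 0.05 | z = 10.82, power >99.9% | z = 11.46, power >99.9% |
| 42% v 45% (OR 1.13) | 0.05/3 | z = 5.30, power 99.8% | z = 5.61, power 99.9% |
| 45% v 47% | 0.05/3 | z = 3.51, power 86.8% | z = 3.72, power 90.7% |
| 47% v 49% | 0.05/3 | power 86.6% | power 90.6% |

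For 45% v 47%, other divisors give 94.0% and 96.1% at alpha 0.05, and 80.9% and 86.0% at 0.05/6. Simulation with a practice random intercept (ICC 1%) and a practice-stratified test agrees to within about one percentage point.

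**Subgroups.** Their sizes are not in the available text, so that claim cannot be checked at either total. At unadjusted alpha 0.05, 90% power for 42% v 47% needs 4 x (1.960 + 1.282)^2 x (0.2436 + 0.2491/3) / 0.05^2, or about 5,490 subjects. That is 9.0% of 61,212 or 8.0% of 68,640. The choice of total therefore decides the claim only for a subgroup whose share lies between those two values.

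**The case for a change.** The best case for a correction is that the portal-user reading is the natural one. The neighbouring sentences are about portal users. The figure cannot be the index total, which is given separately, and it is far below the registry count. On that reading 1,248, 2.38 and 145,684 agree closely at 49 practices (49 x 1,248 x 2.38 = 145,542, within 0.1%) and disagree at 55. Pairing a per-practice figure from a smaller practice count with the maximum count would also sit badly with the plan's description of its power estimates as conservative. Under the plan's own 2-point steps, per-contrast power would be about 87% instead of 91%.

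Part of this stands. The text does not show how the four figures fit together, and the portal-user reading is plausible. The rest goes too far. The 49-practice explanation is a back-calculation. The 2-point steps carry no power claim in the plan, and the values shown omit the planned adjustment for prior-year vaccination and other covariates. Restating the total as 61,200 would add a minimum index count that the plan never gives, and would move further from the registry figures.

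**Conclusion.** No change to the plan follows. The gap between 61,212 and 68,640 (7,428 subjects, 12.1%) exists only if 145,684 counts portal users and 1,248 was derived from it, and the available text says neither. A floor of 145,684, a ceiling of 55 practices and an estimate of 68,640 can all be true together. The user base implied by the registry size and the 59% share leaves room for the 163,363 users required, provided that share applies roughly to the registry.

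No power statement that can be checked turns on the choice: the pooled contrast in all users and the odds ratio of 1.13 both have at least 99.8% power at either total. These values assume within-practice randomisation, a Bonferroni divisor of three for consecutive arms, and no covariate adjustment. The subgroup claim could not be checked.

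The trial randomises an existing registry, so 68,640 is not a recruitment target, and the number analysed will be whatever the eligibility and family rules yield. What is left is a missing unit and an unnamed simulation total. Naming them would help a reader but would change nothing in enrolment, randomisation or analysis.
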